## 7.2.8.2 Drug screening and alcohol breath test

See Appendix A - Schedule of Events for the timepoints of assessment. All study participants will undergo a drug screen and an alcohol breathalyzer test on Visit 1 and Visit 2.

## **7.2.8.3**Exhaled carbon monoxide (eCO)

See Appendix A - Schedule of Events for the timepoints of assessment. An eCO measurement will be performed using a carbon monoxide breath monitor on Visit 1 and Visit 2. For this procedure, study participants must first inhale fully and exhale steadily into the carbon monoxide breath monitor for at least 10 seconds.

## **7.2.8.4**Skin prick test (SPT)

See Appendix A - Schedule of Events for the timepoints of assessment. SPT will be carried out according to applicable SOP using the Test Applicator Application and a standard panel of allergens, including seasonal allergens such as major trees, grass, ragweed and perennial allergens including cat, dog and dust mite will be tested.

## 7.2.8.5 Urine cotinine

See Appendix A - Schedule of Events for the timepoints of assessment. A urine cotinine screen will be performed on Visit 1 and Visit 2.

## 7.2.8.6 Plasma nicotine samples

See Appendix A - Schedule of Events for the timepoints of assessment.

- a) Sample collection
  - 1 x 7 mL of blood will be collected at each time point in pre-chilled K3EDTA vacutainers.
  - Samples will be sequentially collected by direct venipuncture or catheter and processed in a timely manner as per appropriate Analytical Method Information Sheet (AMIS).
  - The labels for all biological sample collection and storage containers will contain, at a minimum:
    - Subject number
    - Study number
    - Collection date
    - Scheduled collection time (study hour)
- b) Sample processing
  - Samples will be cooled in an ice bath or cooling device until processed by centrifuging at approximately 3000 rpm (+/- 50 rpm) at 4°C (± 4°C) for 15 minutes and then placed into an ice bath or cooling device. Samples that are disturbed during the sampling process will be re-spun under the same conditions in an attempt to obtain the maximum amount of plasma from each sample.
  - The time between blood collection and placement in the centrifuge will not exceed 30 minutes (+/- 15 mins).

#### P1-CMS-01-US

Final 2.0 Amendment 1.0, 22-May-2017

Related to PMI RD WKI 000759 CSP

- Plasma will be evenly divided and transferred into duplicate 5 mL polypropylene tubes and maintained in the ice bath or cooling device.
- A minimum of 1.5 mL of plasma is required for each aliquot.
- Samples will then be stored at approximately -20°C (±10°C) until shipment to the bioanalytical laboratory.
- The time between the start of centrifugation and placement in freezer will not exceed 1 hour (+/- 15 mins).
- In cases where the volume of plasma harvested from the blood sample is not sufficient to meet the minimum volume requirement as indicated by the bioanalytical facility, the first polypropylene tube will be filled to meet the minimum volume requirement, and any remaining plasma will be transferred to the second polypropylene tube.
- c) Sample shipment
  - The clinical staff will inventory the samples for Group 1 (smokers) and Group 2 (never smokers) which are to be shipped to the bioanalytical laboratory. Each shipment will contain a complete set of samples for each group. The complete set of samples for Group 1 and 2 will be sent first. The second set of samples for Group 1 and 2 will not be shipped until the status of the first shipment is determined. The inventory record will accompany the plasma samples as per SOPs.
  - The samples will be packed in ample dry ice within a Styrofoam container to ensure the samples will remain frozen for at least 72 hours and shipped via express delivery to the bioanalytical facility. Temperature during shipment is recommended to be monitored, using appropriate devices for the shipment. Written notification of sample shipment will be communicated to the bioanalytical facility and Sponsor. The samples will be tracked to ensure arrival in a safe and timely manner.
  - The shipment will be accompanied by logs identifying the:

study number, protocol number, number of subjects, number of samples included in the shipment and sample collection log sheets.

#### **Confidentiality Statement**

Data and information contained in this document are considered to constitute trade secrets and confidential commercial information, and the legal protections provided to such trade secrets and confidential information are hereby claimed under the provisions of applicable law. No part of this document may be publicly disclosed without the written consent of Philip Morris Products S.A.

P1-CMS-01-US

Final 2.0 Amendment 1.0, 22-May-2017

Page 64 of 106

CSP

Related to PMI RD WKI 000759

- Documentation noting the conditions of the samples upon arrival at the bioanalytical laboratory and whether the amount of dry ice remaining is adequate or inadequate will be returned to the clinic.
- Temperature during shipment is recommended to be monitored, using appropriate devices for the shipment.
- The samples will be shipped to:

- d) Bioanalytical sample analysis
  - The Nicotine plasma concentrations will be measured using validated LC/MS/MS bioanalytical method and according to the Sannova Analytical Inc's Standard Operating Procedures and FDA guidelines and applicable regulatory requirements.

## 7.2.8.7 Saccharin transit time test

See Appendix A - Schedule of Events for the timepoints of assessment. NMC rate will be assessed using saccharin transit time. Before performing the test, each study study participant will spend approximately 15 minutes acclimatizing to the environment of the clinic. A 1-2 mm particle of saccharin will be placed under direct vision, approximately 1 cm behind the anterior end of the inferior turbinate. The position of the study participant's head should be flexed approximately 10° by visual assessment. The study participant will be instructed not to sniff, sneeze, cough, eat or drink and instructed to remain in a seated position for the duration of the test. If possible, the study participant will also be instructed not to speak or engage in any other activities that would disrupt the evaluation. The saccharin transit time will be determined as

#### **Confidentiality Statement**

Philip Morris Products SA

Clinical Study Protocol

Confidential

P1-CMS-01-US

Final 2.0 Amendment 1.0, 22-May-2017

Page 65 of 106

Related to PMI\_RD\_WKI\_000759

the elapsed time in minutes and seconds from placement of the saccharin until the time the study participant perceives a sweet taste.

In case there is no response, the test will be terminated after 60 minutes. The study participant will then have a direct application of saccharin on their tongue to ensure that they can taste the saccharin.

# 7.2.8.8 Nasal scraping, sical assessment and biological specimen collections for further analysis

See Appendix A - Schedule of Events for the timepoints of assessment.

Nasal scraping of the inferior turbinate of both nostrils will be performed on all 14 study participants as described in the separate document "Method establishment to obtain human nasal epithelial sample using the Rhino-probe".

For 4 study participants, nasal scraping (left nostril with method 1, right with method 2) will be performed and cell samples will be collected, processed, appropriately labeled and shipped by the study site as per the "Method establishment to obtain human nasal epithelial sample using the Rhino-probe" to the appropriate laboratory for further histological assessment.

For the 10 remaining study participants, 5 will undergo nasal scraping using method 1, and 5 using method 2. For all 10 study participants, cell sample from one nostril will be added into one buffer and cell sample from the other nostril into a second buffer. Samples will be collected, processed, appropriately labeled and shipped by the study site as per the "Method establishment to obtain human nasal epithelial sample using the Rhino-probe" to the appropriate laboratory for subsequent RNA quantity and quality analysis.

RNA quantity and quality will be assessed as per the Sponsor internal laboratory SOPs. RNA from the nasal sample will be extracted. Then a quantification step will occur using a Nanodrop 1000 instrument (TermoFisher scientific).

The quality will be assessed by using a Bioanlayzer 2100 (Agilent Technologies): the Bioanalyzer delivers a mark from 1 to 10 (10 is the best) to give an idea of the quality and integrity of the RNA (RIN value stands for RNA integrity Number).

# 7.3 Laboratory Assessments

7.3.1 Hematology, clinical chemistry, urine analysis and serology

For hematology, clinical chemistry and virology, up to 22.5 mL of blood per assessment will be needed. The following parameters will be measured:

The blood samples will be sent to LabCorp Raritan for analysis.

A labeling system will be devised such that each sample is distinguishable from all others. Each collection label will contain the following information: 1) study protocol number, 2) sample type, 3) study participant number, and 4) date and time of collection.

Hematology	Clinical Chemistry
• Hematocrit	Albumin
• Hemoglobin	Total protein
• Mean corpuscular hemoglobin (MCH)	• Alkaline phosphatase (AP)
• Mean corpuscular hemoglobin concentration (MCHC)	• Alanine aminotransferase (ALT)
• Mean corpuscular volume (MCV)	• Aspartate aminotransferase (AST)
Platelet count	• Blood urea nitrogen (BUN)
• Red blood cell (RBC) count	• Creatinine
• White blood cell (WBC) count	Fasting Glucose
• Differential WBC count:	• Fibrinogen
Neutrophils	• Gamma-glutamyl transferase (GGT)
• Basophils	• Lactate dehydrogenase (LDH)
• Eosinophils	Potassium
1	• Sodium
Lymphocytes	• Total and direct bilirubin
Monocytes	• Total cholesterol
	Triglycerides

#### Table 2 - Hematology and clinical chemistry parameters

#### **Confidentiality Statement**

Final 2.0 Amendment 1.0, 22-May-2017

Page 67 of 106

Related to PMI\_RD\_WKI\_000759

The following parameters will be analyzed semi-quantitatively in urine:

- pH
- Bilirubin
- Glucose
- Nitrite
- Red blood cell traces
- Protein
- Specific gravity

A test for Hepatitis B surface antigen, hepatitis C virus and human immunodeficiency virus (anti-HIV1/2) will be done at Visit 1.

# 7.4 Volume of blood sample

After enrollment, a total of four (4) blood samples (28 mL total volume) will be collected for nicotine analysis.

A total of 50.5 mL of blood will be collected for each subject.

# 8 ADVERSE EVENTS

## 8.1 Definitions

## 8.1.1 Adverse Events

For the purpose of this study an AE is defined as any untoward medical occurrence that may present itself during the conduct of a study and which may or may not have a causal relationship with the study procedures. An AE can therefore be any unfavorable and unintended sign (including an abnormal laboratory finding), symptom or disease.

## 8.1.2 Serious Adverse Events

A serious adverse event (SAE) is defined as an AE that:

- Results in death.
- Is life-threatening.
- Requires inpatient hospitalization or prolongation of existing hospitalization.
- Results in persistent or significant disability/incapacity, or
- Is a congenital anomaly/birth defect.
- Is an important medical event.

Important medical events that may not result in death, be life-threatening, or require hospitalization may be considered an SAE when, based on appropriate medical judgment, they may jeopardize the subject or the subject may require medical or surgical intervention to prevent one of the outcomes listed in the above definitions.

"Life-threatening" means that the subject was at immediate risk of death from the event. It might have caused death if it had occurred in a more serious form.

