## 8.2.3 Intensity of Adverse Event

- Mild: Awareness of symptoms but easily tolerated, no disruption of normal activities.
- Moderate: Discomfort enough to cause interference with usual activity.
- Severe: Incapacitating with inability to work or do usual activity.

Change in severity (intensity) needs to be documented.

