# 8.3 Reporting of Serious Adverse Events

Any SAE observed during the period of collection by any of the parties involved in this study (including the Investigational site personnel) must be reported by that party within 24 hours of first awareness to the sponsor representative. The Sponsor representative will be notified in writing (SAE report form) within 24 hours of when a SAE is first recognized or reported by contacting:

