### 5.5.4.2 Safety analysis

Vital signs (systolic blood pressure, diastolic blood pressure, pulse rate and respiratory rate) will be summarized by total number of observations (n), mean, median, standard deviation, quartiles (Q1 and Q3) and minimum and maximum values.

An overall summary of AEs will be presented by smoker and never smoker groups showing the number of events and percent of study participants who experienced AEs, SAEs, severe AEs and AEs leading to study discontinuation.

A summary of AEs by System Organ Class (SOC) and Preferred Term (PT) according to Medical Dictionary for Regulatory Activities (MedDRA) by smoker and never smoker groups will be presented.

Each parameter of hematology, clinical chemistry and urine will be summarized over time by smoker and never smoker group thought total number of observations (n), mean, median, standard deviation, quartiles (Q1 and Q3) and minimum and maximum values. Number (n) and frequency distribution (%) of normal and abnormal values will also be present by each parameter.

All safety analyses will be performed for the safety dataset only.

Vital signs measures will be presented for safety dataset in Table A 10 and listed in Listing 12

Incidence and frequency distribution of AEs, SAEs, AEs with reasonable possibility of relationship with study drug will be presented in **Table A 11** and **Table A 12**. All adverse events and serious adverse events will also be listed by subject in **Listing 13** and **Listing 14**.

Regarding laboratory parameters, results of hematology, chemistry and urinalysis will be presented for safety dataset in **Table A 13**, **Table A 14** and **Table A 15** and listed by subject in **Listing 15**. Results on serology at visit 1 will be presented in **Table A 16**.

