#### Table A 11 – Overall summary of adverse events – Safety population

	Smoker (n=xx)		Never sm (n=xx)	noker
	n (%)	nAEs	n (%)	nAEs
Any adverse event, n (%) Any serious adverse event, n (%)				

Any severe adverse event, n (%) Any adverse event leading to study discontinuation, n (%)

n (%) = Number (percent) of subjects. nAE = Number of adverse events.

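### The second sentence of the life-threatening definition adds a hypothetical-severity test that is either redundant or widens the SAE criterion, and the protocol does not say which

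*Protocol*

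**What the plan says.** Protocol section 8.1.2 lists six criteria that make an adverse event serious, one of which is "Is life-threatening". Below the list, two consecutive sentences explain that criterion. The first says that it "means that the subject was at immediate risk of death from the event". The second says "It might have caused death if it had occurred in a more serious form". The second sentence contains no negation and no word linking it to the first.

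Intensity is handled separately. Section 8.2.3 grades events as mild, moderate or severe, and the mild grade is "Awareness of symptoms but easily tolerated, no disruption of normal activities".

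Section 8.3 attaches a reporting duty to the SAE label: an SAE "must be reported by that party within 24 hours of first awareness to the sponsor representative". In the SAP, section 5.5.4.2 plans a summary by group of the "number of events and percent of study participants who experienced AEs, SAEs, severe AEs and AEs leading to study discontinuation". Table A 11 carries a row for "Any serious adverse event, n", and Listing 14 has a separate column for the life-threatening criterion.

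**The concern.** The first sentence asks what happened to the participant. The second asks what might have happened had the event been worse. Many events that are harmless as they occur have a severe form that can kill, so the two questions can be answered differently for the same event. An investigator who takes the second sentence as the explanation of the term, or as another way to meet it, applies a wider criterion than one who relies on the first.

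Four things in the plan depend on the answer:

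- **Sponsor reporting.** Every SAE goes to the sponsor representative within 24 hours (Protocol synopsis, safety reporting; section 8.3).
- **Follow-up.** Non-serious events still open after the 1-day Safety Follow-Up Period are recorded as ongoing and not pursued. SAEs are followed until they resolve, stabilise or are explained (sections 8.2.2 and 9.3).
- **Tabulated results.** Table A 11 gives the number of participants with an SAE and the number of events, by smoking group.
- **Listed results.** Listing 14 shows which seriousness criterion was met.

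A hypothetical test also sits badly with the protocol's separation of seriousness from intensity, because it makes seriousness depend on an intensity that the event did not have.

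**Working it through.** The plan gives no figure to reproduce. The check compares the possible readings and then sizes one reclassification.

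**Step 1. The two tests.** Let A be the first sentence (the participant was at immediate risk of death from the event as it occurred). Let H be the second (the event could have been fatal in a more serious form).

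**Step 2. How they may combine.** Nothing else in the protocol or SAP explains the term, so three readings are open.

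- *Both required (A and H).* An event that put the participant at immediate risk of death could also have killed in a worse form, so A carries H with it. The joint test reduces to A, and the second sentence is redundant.
- *Either suffices (A or H).* By the same reasoning this reduces to H, which is wider than A.
- *The second explains the first (H in place of A).* This is again H.

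The three readings therefore give two outcomes: the second sentence does nothing, or it widens the criterion.

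**Step 3. Is the wider test needed as a safety net?** No. Section 8.1.2 already has a criterion for important medical events, which brings in, on medical judgment, events that may endanger the participant or need intervention to prevent a listed outcome.

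**Step 4. Where the outcomes diverge.** Take an event that meets the mild grade in section 8.2.3: noticed, easily tolerated, no disruption of activities. It is hard to see such an event meeting A. It can meet H whenever its severe form could be fatal. Under A it is a non-serious AE. Under H it is an SAE, with the reporting and follow-up described above.

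**Step 5. Scale of one reclassification.** Protocol section 12.2 plans 7 smokers and 7 never smokers, and the safety population is all enrolled participants.

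- Within a group: 1/7 = 14.3%, so one participant moves the group's SAE percentage from 0% to 14.3%.
- Across both groups: 1/14 = 7.1%.
- Precision: the exact (Clopper-Pearson) upper 95% limit for 0/7 is 1 − 0.025^(1/7) = 41.0%. For 1/7 the lower limit is 1 − 0.975^(1/7) = 0.4% and the upper limit, a beta quantile, is 57.9%. The intervals overlap almost entirely.

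These figures show only what one event does to a denominator of 7. They do not estimate how often reclassification would occur, and Table A 11 plans counts and percentages without intervals.

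**The case against.** The strongest reply is that the first sentence holds the operative definition and is never withdrawn. The second begins with a pronoun that can refer back to the event that already carried immediate risk. Read that way, nothing is widened. This is a fair reading, and it is why a reader who infers that the two sentences flatly contradict each other goes too far. Both tests can be met at once. What stands is that the text does not require this reading, and that under it the second sentence has no purpose.

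A reader might also infer that the definition turns mild procedure events, such as a slight nosebleed after nasal scraping or a faint at blood sampling, into SAEs. The documents do not say so. It would follow only if the second sentence were applied on its own. They give no rate for such events, and section 2.3.2 of the protocol puts procedure risk on a level with routine health examinations.

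Three further limits are sound:

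- Seriousness and severity are separate columns in SAP Listing 13, and Listing 14 shows the criterion that was met. With 14 participants, a mild event marked life-threatening would be visible line by line.
- The 24-hour IRB notice in section 8.3 covers reportable SAEs, so the SAE label alone does not trigger it.
- The first sentence still captures every truly life-threatening event, so the second cannot cause one to be missed.

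Finally, it is tempting to conclude that the word *not* was dropped from an exclusion sentence. Nothing in the protocol or SAP contains the negated form, so this remains conjecture and the point does not rest on it.

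**Conclusion.** Wrong as written, minor severity. The second sentence of the definition is either redundant or an unintended widening of an operative SAE criterion, and the documents do not settle which. The possible consequence is over-classification of non-serious events, with extra 24-hour sponsor reports, extended follow-up and inflated SAE entries in Table A 11 and Listing 14. One reclassified participant is 14.3% of a group.

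That consequence depends on an investigator applying the second sentence by itself, and its likelihood cannot be estimated from the documents. The severity is held down because the error can only be toward over-reporting. It also rests on a judgment, not a stated figure, that few SAEs will arise in 14 healthy men over so short a study. Safety is a secondary, descriptive objective, and no saccharin transit time result is affected.

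**What to change.** Reconcile the two sentences in Protocol section 8.1.2 so that only the actual-risk test applies. Either of these does it:

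- delete the second sentence; or
- reword it as an explicit exclusion, stating that the term does not cover an event that could only hypothetically have been fatal had it been more severe.

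Use the same wording in the instructions for the SAE form, so that the investigator and the sponsor representative apply one test. Table A 11 and Listing 14 need no change.

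The cost is one sentence in the protocol and the matching line in the form instructions. No new data, procedures or participant burden are involved.

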# 8.2 Assessment of Adverse Events

The Principal Investigator or designee is responsible for obtaining, assessing and documenting all AEs during the study.

Any exacerbation/worsening of an AE or pre-existing condition shall be evaluated and recorded.

AEs will be coded at the end of the study in the latest Medical Dictionary for Regulatory Activities (MedDRA) version, preferred term, available at the time of adverse events coding.

## 8.2.1 Collection of Information

Any non-serious AE occurrence during the study must be documented in the subject's medical records in accordance with the Principal Investigator's normal clinical practice and on the AE page of the CRF. SAEs that occur during the study must be documented in the subject's medical record, on the AE CRF, and on the SAE form.

AEs should be collected mainly via face-to-face interview with the subject through spontaneous reporting or by the use of consistent, open, non-directive questions from the PI(s) or designee(s) (e.g., "Have you had any health problems since you were last asked? or "How have you been feeling since you were last asked?"). Information recorded will include: verbatim description of the AE/SAE, start and stop dates, seriousness, severity (intensity), action taken (e.g., whether or not the AE/SAE led to the subject's discontinuation from the study), and outcome (e.g., resolved, stabilized). Information to be recorded about a SAE should also include, whenever possible, onset and resolution dates and times, circumstances leading up to the event, clinical elements such as clinical course, specific vital signs and test results that may explain the pathophysiology of the event, as well as alternative explanations to its occurrence.

Whenever a medically meaningful diagnosis is available to comprise a set of reported signs and/or symptoms, it should be preferentially provided as the AE or SAE term, rather than the individual signs and/or symptoms. Otherwise, each one of those signs and/or symptoms should be reported separately as event terms.

